3.3. Duration of Study

3.3.1. Duration of Treatment

For most participants, treatment will be confined to study day 1. For participants in experimental arm 3 of the phase 2 study, treatment will occur on day 1 and day 29.

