3.4.2.2. Secondary Endpoints

3.4.2.2.1. Safety

- Incidence of MAAEs and SAEs through 30 days post final vaccine administration
- Incidence of MAAEs and SAEs through 6 months post final vaccine administration
- Incidence and severity of solicited local reactogenicity AEs through 1 week after each vaccine administration
- Incidence and severity of solicited systemic reactogenicity AEs through 1 week after each vaccine administration
- Incidence and severity of unsolicited AEs through 30 days post final vaccine administration

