6.3. Safety Assessments

All participants will be monitored for AEs during the study. Assessment of AEs will include the following parameters:

- All MAAEs and SAEs for 6 months after last vaccine administration (related MAAEs and SAEs at any time)
- Solicited local and systemic AEs via diary for 7 days after each vaccine administration (applicable to the phase 1 and phase 2 studies)
- Unsolicited AEs via diary from first dose of study treatment until 30 days after last vaccination (applicable to the phase 1 and phase 2 studies)
- Vital signs
- Body weight
- Physical examinations
- Hematology: CBC with differential
- Chemistry panel: Collection of whole blood for complete metabolic panel (CMP)
- Urinalysis: protein, glucose, and RBCs
- Pregnancy test.

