6.3.2. Unsolicited Adverse Events

Unsolicited AEs will be captured at study visits and by a diary distributed to participants. Diaries for unsolicited AEs will be reviewed at all study visits until 30 days after the last dose of vaccine. A sample diary for the recording of unsolicited events is provided in [Appendix 2](#).

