6.7.1.1. Medical History

At screening, the participant's medical history should be taken as per institutional standards. Otherwise, only the following medical history should be recorded in the eCRF:

- Current symptoms
- Items listed in inclusion/exclusion
- Existing medical conditions.
- Medications/procedures related to existing conditions.
- History of any prior COVID-19 symptoms.
- Vaccination history

Table 10: Schedule of Events: Previously Vaccinated/Infected Participants

Study Period	Prescreening ^a	Baseline/ Screening	Vaccine Administration and Initial Follow-Up					Extended Follow-Up		
			1	8	22	29	36	60	180	365
Study Day	-5 to -1	-5 to -1	1	8	22	29	36	60	180	365
Clinic visit number	Prescreening	Screening	1	2	3	4		5	6	7
Windows (Days)				± 3				± 7		± 14
General Assessments										
Informed consent	X	X								
Inclusion/ exclusion		X								
Demographics		X								
Medical history		X								
Tuberculosis screening ^b		X								
COVID-19 history of disease ^c		X	X	X	X	X		X	X	X
Confirm contraceptive measures		X	X			X				
Physical exam: height, weight ^d		X	X	X	X	X				
Vital signs ^e		X	X	X	X	X				
Concomitant medications		X	X	X	X	X		X	X	
Participant training on AE diaries			X							
Issue diaries for solicited AEs (phase 1 and 2 only) ^f				X			X			
Review and collect solicited AE diary (phase 1 and 2 only) ^f					X			X		
Issue diaries for unsolicited AEs				X						
Review unsolicited AE diary					X	X	X			
Collect unsolicited AE diary								X		

AAHI-SC2 and AAHI-SC3

ImmunityBio, Inc.

Clinical Trial Protocol: COVID-4.015 Version 4

Study Period	Prescreening ^a	Baseline/ Screening	Vaccine Administration and Initial Follow-Up						Extended Follow-Up		
			1	8	22	29	36	60	180	365	
Study Day	-5 to -1	-5 to -1	1	8	22	29	36	60	180	365	
Clinic visit number	Prescreening	Screening	1	2	3	4		5	6	7	
Windows (Days)			± 3					± 7		± 14	
In office AE collection			X	X	X	X		X			
Telephone follow-up							X ^g		X	X	
Vaccine Administration: Phase 1											
Cohort 1A			AAHI-SC2 (25 µg)								
Cohort 1B			AAHI-SC2 (50 µg)								
Cohort 1C			AAHI-SC2 (70 µg)								
Cohort 2A			AAHI-SC3 (25 µg)								
Cohort 2B			AAHI-SC3 (50 µg)								
Cohort 2C			AAHI-SC3 (85 µg)								
Vaccine Administration: Phase 2											
Experimental Arm 1			AAHI-SC2 (dose to be determined [TBD])								
Experimental Arm 2			AAHI-SC3 (dose TBD)								
Experimental Arm 3			AAHI-SC3 (dose TBD)				AAHI- SC3 (dose TBD)				
Control Arm			Janssen/Pfizer-BioNTech vaccine								

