APPENDIX 2. SAMPLE DIARY FOR UNSOLICITED EVENTS

STUDY NUMBER*: _____

Patient Number*	Date of Vaccine Administration	/ /	*To be completed by the site
-----------------	--------------------------------	-----	------------------------------

Please complete this diary every day beginning on the day you receive the first dose of study vaccine until 30 days after you receive the last dose of study vaccine. Each page has space for recording 7 days of information. You will be provided with enough pages to last until 30 days after you receive the last dose of study vaccine. Be sure to bring this diary each time you visit the clinic and refer to this diary when study personnel contact you by telephone for schedule safety follow up assessments.

Unsolicited AEs	Date / /						

Please describe any unusual feelings of discomfort, signs or symptoms that are not specified on the other daily diaries. If you do not experience these feelings, signs, or symptoms, please mark "no additional symptoms to report". For each separate sign and symptom you report in the diary, please note the following:
 
 • How intense it is, either Mild (no interference with activity), Moderate (some interference with activity), or Severe (significant; prevents daily activity) • How long it lasts • Any actions you took to manage the symptoms (for instance, taking medication) 							

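### Table 10's visit window lets arm 3's unsolicited AE diary be collected before the 30 days after dose 2 have passed

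*Combined protocol and SAP*

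**What the plan says.** Section 3.3.1 separates one arm from the rest. "For most participants, treatment will be confined to study day 1", but "For participants in experimental arm 3 of the phase 2 study, treatment will occur on day 1 and day 29".

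The text sets the end of unsolicited AE recording by the last dose:

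- The phase 2 secondary safety endpoint (Section 3.4.2.2.1) is "Incidence and severity of unsolicited AEs through 30 days post final vaccine administration".
- Section 6.3 lists "Unsolicited AEs via diary from first dose of study treatment until 30 days after last vaccination".
- Section 6.3.2 adds: "Diaries for unsolicited AEs will be reviewed at all study visits until 30 days after the last dose of vaccine".
- The sample diary in Appendix 2 tells participants: "You will be provided with enough pages to last until 30 days after you receive the last dose of study vaccine".

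Table 10 sets the end by study day. Its row "Collect unsolicited AE diary" has a single mark, at the day-60 visit, which is also the last in-office AE collection. The next scheduled contact is at day 180, marked as telephone follow-up. Section 7.4.3 limits routine inquiry beyond 30 days after the last dose to serious AEs (SAEs).

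**The concern.** The endpoint is tied to the last dose, but the diary hand-in is tied to the study day and has a tolerance on both sides. For single-dose participants the gap between the two is wide. For arm 3 it is one day, so an early visit within the allowed window collects the diary before the endpoint period is over.

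The protocol does not tie this visit to the date dose 2 was given or restrict its early side for arm 3. It also does not provide for the diary to be kept and returned after an early visit. A site could follow Table 10 exactly and still fall short of the 30 days that the endpoint, Sections 6.3 and 6.3.2 and Appendix 2 require. What is at stake is complete recording of late, milder events after the second dose, in the only arm that has one.

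**Working it through.** **Inputs**

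- Dose 2 in arm 3: day 29 (Section 3.3.1).
- Endpoint period: 30 days after the final dose (Section 3.4.2.2.1).
- Diary collection: day 60 (Table 10). Some marks in neighbouring diary rows look displaced in the text available. However, footnote f places arm 3's solicited-diary collection at day 60, and the unsolicited-diary mark stands in that same column. Day 36 is a telephone contact only.
- Day-60 window: ±7 under two of the three printed headers of Table 10. The third prints ±7 under day 180, so ±3 is kept as an alternative.
- Day-29 window: ±3 is an assumption, because the extent of the merged cell is lost.

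**Formulas**

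- End of period = dose-2 day + 30.
- Days lost = max(0, end of period − collection day).

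**Nominal schedule.** 29 + 30 = 59, and 60 − 29 = 31. Collection on day 60 covers the period by one day.

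**Allowed range.** Under ±7 the visit may fall on days 53 to 67 (15 days). Under ±3 it may fall on days 57 to 63 (7 days).

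| Dose 2 on day | Period ends | Day 60 is this many days after dose 2 | ±7: short visit days | ±7: maximum loss | ±7: mean loss | ±3: short visit days | ±3: maximum loss |
|---|---|---|---|---|---|---|---|
| 26 | 56 | 34 | 53–55 (3 of 15) | 3 days | 6/15 = 0.4 | none | 0 days |
| 29 | 59 | 31 | 53–58 (6 of 15) | 6 days | 21/15 = 1.4 | 57–58 (2 of 7) | 2 days |
| 32 | 62 | 28 | 53–61 (9 of 15) | 9 days | 45/15 = 3.0 | 57–61 (5 of 7) | 5 days |

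The means assume visits spread evenly over the window, which the documents neither state nor support. The numerators are sums of daily losses, for example 6+5+4+3+2+1 = 21. As shares of the 30 days, the maximum losses under ±7 are 3/30 = 10%, 6/30 = 20% and 9/30 = 30%. Counting the dosing day as day 1 of the 30 lowers each non-zero maximum by one day.

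**Single-dose participants.** 1 + 30 = 31, and the earliest collection under ±7 is day 53. The margin is 53 − 31 = 22 days, so nothing is lost.

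**Total observation in arm 3.** Even with the earliest visit, day 53 is 53 − 1 = 52 days after the first dose. The required period in the single-dose arms is 30 days.

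**The case against.** The strongest reply is that the plan already requires the full 30 days. The endpoint, the safety sections and the participant's own instructions all say so, and the nominal visit satisfies them. On this view an early collection would be a site error rather than a design fault. It stands to this extent: the endpoint is not cut short by design, and a site that puts the text ahead of the table would wait. But Table 10 is the schedule that sites work from, and it permits the early visit without qualification.

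Three further limits also stand. Medically attended AEs (MAAEs) and SAEs are recorded for 6 months (Sections 6.3 and 7.2), so the 30-day endpoint for those events is untouched. Solicited reactions have their own 7-day diary. The endpoint is secondary and descriptive, and Section 8.3.1 plans no statistical comparison of the phase 2 arms.

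A reader might infer that arm 3, with the most exposure, gets the shortest follow-up and so looks safer than the other arms. The documents do not support this. Unsolicited AEs are recorded from the first dose, so arm 3 accrues events over at least 52 days under the ±7 reading, against a 30-day period in the single-dose arms. For participant-level incidence, that longer observation is more likely to raise arm 3's figure than to lower it.

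**Conclusion.** The point holds as a conflict between Table 10's window and the 30-day rule, confined to arm 3 (30 planned participants). With dose 2 on day 29, up to 6 of the last 30 days can go unrecorded under a ±7 window, or up to 2 under ±3. If dose 2 may also move by ±3 days, the maximum under ±7 runs from 3 to 9 days and the evenly-spread mean from 0.4 to 3.0 days. The 9-day figure needs the latest dose 2 and the earliest visit together.

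The events at risk are non-serious, non-medically-attended unsolicited AEs in the closing days after dose 2. A participant seen on or after the 30th day following dose 2 loses nothing. Both window readings come from a table whose merged cells are lost, so they should be checked against the laid-out page. A loss remains possible under either day-60 window when dose 2 is on day 29. This is a small defect, worth correcting because it is cheap to correct.

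**What to change.** Reconcile Table 10 with the 30-day rule by adding one footnote for phase 2 arm 3: the day-60 visit and the unsolicited diary collection take place no earlier than 30 days after the actual date of dose 2, with the existing upper limit of the window kept. Table 10 already has arm-3-specific footnotes (f, g and m), so this fits its structure.

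The cost is the early part of arm 3's visit window. Under ±7, days 59 to 67 remain if dose 2 was on day 29 (9 of 15 days), and days 62 to 67 if it was on day 32 (6 of 15). If the day-60 window is ±3, a day-32 dose would leave only days 62 and 63. No visit is added, dosing does not change, and the other arms keep their schedule.

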6.7.2. Study Period(s)

Procedures and evaluations to be performed during visits should be performed with the site's standard-of-care protocol.

6.7.3. End-of-Study Procedures and Evaluations

End-of-study (EOS) is 1 year after the first vaccine injection. All participants receiving ≥ 1 dose of vaccine and discontinuing the study for any reason will complete a discontinuation visit approximately 30 days after they last received treatment. For participants who discontinue prior to study day 29, the discontinuation visit should include all assessments listed for Day 29 in [Table 10](#). For participants who discontinue prior to day 60, the discontinuation visit should include all assessments listed for day 60. If a participant is unable to travel for the EOS visit, the participant will be required to visit his/her primary care provider for safety labs and a physical exam. Research staff will obtain records and follow up with a phone call.

6.8. Concomitant Medications

All concomitant medications should be recorded in the participant's source documents and in the eCRF from the time of signature of the ICF until the EOS visit. The following concomitant medications are of special interest, and should be recorded until the EOS visit unless specified for a longer period below:

- Concomitant medications to manage SAEs attributed to COVID-19 and the study treatment from initiation of SAE until resolved (returned to baseline), recovered from sequelae, or death (due to the SAE).
- Concomitant medications given in supportive care for COVID-19 symptoms or treatment-related AEs including, but not limited to:
 - Analgesics

6.9. Participant Access to Study Medications at Close of Study

At the close of the study, a participant may be eligible to enroll in other open clinical trials. The investigational product will not be available to the participant once he/she has completed the EOS visit.

7. ADVERSE EVENT MONITORING AND REPORTING

AEs will be recorded and monitored and, when appropriate, reported to SAHPRA and others involved in an investigation (sponsors, IRBs, and investigators) in accordance with existing statutes. In addition, to assist in monitoring safety and making required reports, AEs will be categorized in accordance with the Guidance for Industry: Toxicity Grading Scale for Healthy Adult and Adolescent Volunteers Enrolled in Preventive Vaccine Clinical Trials (2007). These scales are described in more detail in the following sections.

7.1. Guidance for Industry: Toxicity Grading Scale for Healthy Adult and Adolescent Volunteers Enrolled in Preventive Vaccine Clinical Trials (2007)

The enrollment of healthy volunteers warrants a very low tolerance for risk. The Guidance for Industry: Toxicity Grading Scale for Healthy Adult and Adolescent Volunteers Enrolled in Preventive Vaccine Clinical Trials (2007) will be used to assess the severity of clinical and laboratory abnormalities in healthy adult volunteers enrolled in this study. AEs will be graded according to the following tables from The Guidance for Industry: Toxicity Grading Scale for Healthy Adult and Adolescent Volunteers Enrolled in Preventive Vaccine Clinical Trials (2007).

Table 11: Clinical Abnormalities: Local Reaction to Injectable Products

Local Reaction to Injectable Product	Mild (Grade 1)	Moderate (Grade 2)	Severe (Grade 3)	Potentially Life Threatening (Grade 4)
Pain	Does not interfere with activity	Repeated use of non-narcotic pain reliever > 24 hours or interferes with activity	Any use of narcotic pain reliever or prevents daily activity	Emergency room (ER) visit or hospitalization
Tenderness	Mild discomfort to touch	Discomfort with movement	Significant discomfort at rest	ER visit or hospitalization
Erythema/Redness *	2.5 – 5 cm	5.1 – 10 cm	> 10 cm	Necrosis or exfoliative dermatitis
Induration/Swelling **	2.5 – 5 cm and does not interfere with activity	5.1 – 10 cm or interferes with activity	> 10 cm or prevents daily activity	Necrosis

* In addition to grading the measured local reaction at the greatest single diameter, the measurement should be recorded as a continuous variable.

** Induration/Swelling should be evaluated and graded using the functional scale as well as the actual measurement.

Table 12: Clinical Abnormalities: Vital Signs

Vital Signs *	Mild (Grade 1)	Moderate (Grade 2)	Severe (Grade 3)	Potentially Life Threatening (Grade 4)
Fever (°C) ** (°F) **	38.0 – 38.4 100.4 – 101.1	38.5 – 38.9 101.2 – 102.0	39.0 – 40 102.1 – 104	> 40 > 104
Tachycardia - beats per minute	101 – 115	116 – 130	> 130	ER visit or hospitalization for arrhythmia
Bradycardia - beats per minute***	50 – 54	45 – 49	< 45	ER visit or hospitalization for arrhythmia
Hypertension (systolic) - mm Hg	141 – 150	151 – 155	> 155	ER visit or hospitalization for malignant hypertension
Hypertension (diastolic) - mm Hg	91 – 95	96 – 100	> 100	ER visit or hospitalization for malignant hypertension
Hypotension (systolic) – mm Hg	85 – 89	80 – 84	< 80	ER visit or hospitalization for hypotensive shock
Respiratory Rate – breaths per minute	17 – 20	21 – 25	> 25	Intubation

* Participant should be at rest for all vital sign measurements.

** Oral temperature; no recent hot or cold beverages or smoking.

*** When resting heart rate is between 60 – 100 beats per minute. Use clinical judgement when characterizing bradycardia among some healthy participant populations, for example, conditioned athletes.

Table 13: Clinical Abnormalities: Systemic

Systemic (General)	Mild (Grade 1)	Moderate (Grade 2)	Severe (Grade 3)	Potentially Life Threatening (Grade 4)
Nausea/vomiting	No interference with activity or 1 – 2 episodes/24 hours	Some interference with activity or > 2 episodes/24 hours	Prevents daily activity, requires outpatient IV hydration	ER visit or hospitalization for hypotensive shock
Diarrhea	2 – 3 loose stools or < 400 gms/24 hours	4 – 5 stools or 400 – 800 gms/24 hours	6 or more watery stools or > 800 gms/24 hours or requires outpatient IV hydration	ER visit or hospitalization
Headache	No interference with activity	Repeated use of non-narcotic pain reliever > 24 hours or some interference with activity	Significant; any use of narcotic pain reliever or prevents daily activity	ER visit or hospitalization
Fatigue	No interference with activity	Some interference with activity	Significant; prevents daily activity	ER visit or hospitalization
Myalgia	No interference with activity	Some interference with activity	Significant; prevents daily activity	ER visit or hospitalization
Systemic Illness	Mild (Grade 1)	(Moderate(Grade 2)	Severe (Grade 3)	Potentially Life Threatening (Grade 4)
Illness or clinical adverse event (as defined according to applicable regulations)	No interference with activity	Some interference with activity not requiring medical intervention	Prevents daily activity and requires medical intervention	ER visit or hospitalization

Table 14: Laboratory Abnormalities: Serum

Serum *	Mild (Grade 1)	Moderate (Grade 2)	Severe (Grade 3)	Potentially Life Threatening (Grade 4)**
Sodium – Hyponatremia mEq/L	132 – 134	130 – 131	125 – 129	< 125
Sodium – Hypernatremia mEq/L	144 – 145	146 – 147	148 – 150	> 150
Potassium – Hyperkalemia mEq/L	5.1 – 5.2	5.3 – 5.4	5.5 – 5.6	> 5.6
Potassium – Hypokalemia mEq/L	3.5 – 3.6	3.3 – 3.4	3.1 – 3.2	< 3.1
Glucose – Hypoglycemia mg/dL	65 – 69	55 – 64	45 – 54	< 45
Glucose – Hyperglycemia Fasting – mg/dL Random – mg/dL	100 – 110 110 – 125	111 – 125 126 – 200	>125 >200	Insulin requirements or hyperosmolar coma
Blood Urea Nitrogen BUN mg/dL	23 – 26	27 – 31	> 31	Requires dialysis
Creatinine – mg/dL	1.5 – 1.7	1.8 – 2.0	2.1 – 2.5	> 2.5 or requires dialysis
Calcium – hypocalcemia mg/dL	8.0 – 8.4	7.5 – 7.9	7.0 – 7.4	< 7.0
Calcium – hypercalcemia mg/dL	10.5 – 11.0	11.1 – 11.5	11.6 – 12.0	> 12.0
Magnesium – hypomagnesemia mg/dL	1.3 – 1.5	1.1 – 1.2	0.9 – 1.0	< 0.9
Phosphorous – hypophosphatemia mg/dL	2.3 – 2.5	2.0 – 2.2	1.6 – 1.9	< 1.6
CPK – mg/dL	1.25 – 1.5 x ULN***	1.6 – 3.0 x ULN	3.1 – 10 x ULN	> 10 x ULN
Albumin – Hypoalbuminemia g/dL	2.8 – 3.1	2.5 – 2.7	< 2.5	--

Serum *	Mild (Grade 1)	Moderate (Grade 2)	Severe (Grade 3)	Potentially Life Threatening (Grade 4)**
Total Protein – Hypoproteinemia g/dL	5.5 – 6.0	5.0 – 5.4	< 5.0	--
Alkaline phosphate – increase by factor	1.1 – 2.0 x ULN	2.1 – 3.0 x ULN	□ 3.1 – 10 x ULN	> 10 x ULN
Liver Function Tests –ALT, AST increase by factor	1.1 – 2.5 x ULN	2.6 – 5.0 x ULN	5.1 – 10 x ULN	> 10 x ULN
Bilirubin – when accompanied by any increase in Liver Function Test increase by factor	1.1 – 1.25 x ULN	1.26 – 1.5 x ULN	1.51 – 1.75 x ULN	> 1.75 x ULN
Bilirubin – when Liver Function Test is normal; increase by factor	1.1 – 1.5 x ULN	1.6 – 2.0 x ULN	2.0 – 3.0 x ULN	> 3.0 x ULN
Cholesterol	201 – 210	211 – 225	> 226	---
Pancreatic enzymes – amylase, lipase	1.1 – 1.5 x ULN	1.6 – 2.0 x ULN	2.1 – 5.0 x ULN	> 5.0 x ULN

* The laboratory values provided in the tables serve as guidelines and are dependent upon institutional normal parameters. Institutional normal reference range should be provided to demonstrate that they are appropriate.

** The clinical signs or symptoms associated with laboratory abnormalities might result in characterization of the laboratory abnormalities as Potentially Life Threatening (Grade 4). For example, a low sodium value that falls within a grade 3 parameter (125-127 mE/L) should be recorded as a grade 4 hyponatremia event if the participant had a new seizure associated with the low sodium value.

***ULN" is the upper limit of the normal range.

Table 15: Laboratory Abnormalities: Hematology

Hematology *	Mild (Grade 1)	Moderate (Grade 2)	Severe (Grade 3)	Potentially Life Threatening (Grade 4)
Hemoglobin (Female) - gm/dL	11.0 – 12.0	9.5 – 10.9	8.0 – 9.4	< 8.0
Hemoglobin (Female) change from baseline value - gm/dL	Any decrease – 1.5	1.6 – 2.0	2.1 – 5.0	> 5.0
Hemoglobin (Male) - gm/dL	12.5 – 13.5	10.5 – 12.4	8.5 – 10.4	< 8.5
Hemoglobin (Male) change from baseline value – gm/dL	Any decrease – 1.5	1.6 – 2.0	2.1 – 5.0	> 5.0
WBC Increase - cell/mm ³	10,800 – 15,000	15,001 – 20,000	20,001 – 25,000	> 25,000
WBC Decrease - cell/mm ³	2,500 – 3,500	1,500 – 2,499	1,000 – 1,499	< 1,000
Lymphocytes Decrease - cell/mm ³	750 – 1,000	500 – 749	250 – 499	< 250
Neutrophils Decrease - cell/mm ³	1,500 – 2,000	1,000 – 1,499	500 – 999	< 500
Eosinophils - cell/mm ³	650 – 1500	1501 – 5000	> 5000	Hypereosinophilic
Platelets Decreased - cell/mm ³	125,000 – 140,000	100,000 – 124,000	25,000 – 99,000	< 25,000
PT – increase by factor (prothrombin time)	1.0 – 1.10 x ULN**	1.11 – 1.20 x ULN	1.21 – 1.25 x ULN	> 1.25 ULN
PTT – increase by factor (partial thromboplastin time)	1.0 – 1.2 x ULN	1.21 – 1.4 x ULN	1.41 – 1.5 x ULN	> 1.5 x ULN
Fibrinogen increase - mg/dL	400 – 500	501 – 600	> 600	--
Fibrinogen decrease - mg/dL	150 – 200	125 – 149	100 – 124	< 100 or associated with gross bleeding or disseminated intravascular coagulation (DIC)

* The laboratory values provided in the tables serve as guidelines and are dependent upon institutional normal parameters.

Institutional normal reference ranges should be provided to demonstrate that they are appropriate.

** "ULN" is the upper limit of the normal range.

Table 16: Laboratory Abnormalities: Urine

Urine *	Mild (Grade 1)	Moderate (Grade 2)	Severe (Grade 3)	Potentially Life Threatening (Grade 4)
Protein	Trace	1+	2+	Hospitalization or dialysis
Glucose	Trace	1+	2+	Hospitalization for hyperglycemia
Blood (microscopic) – red blood cells per high power field (rbc/hpf)	1 - 10	11 – 50	> 50 and/or gross blood	Hospitalization or packed red blood cells (PRBC) transfusion

* The laboratory values provided in the tables serve as guidelines and are dependent upon institutional normal parameters. Institutional normal reference ranges should be provided to demonstrate that they are appropriate.

